8.7. Supportive Care

No specific supportive medication is advised with nivolumab. Recommended supportive care for patients with autoimmune complications or infusion reactions are set out in section 8.4.

Anti-emetics, anaglesics, antibiotics, electrolyte and fluid replacement, anti-coagulants and antiplatelet agents may be given in accordance with local policies and as clinically indicated.

Medications used to treat pre-existing co-morbidities can be continued, with the exception of immune-suppressants (as set out in section 8.8). Supportive/prophylactic medications recommended to continue post previous chemotherapy regimes, e.g. acyclovir, may also be continued.

GCSF may be given as per local policy for neutropenia persisting for greater than 7 days.

Any supportive medications given should be clearly documented in the patient notes.

8.8. Contraindications

According to the IB for nivolumab, no drugs are contraindicated during nivolumab treatment.

Form

Form

Form

Form

Any other systemic anti-cancer therapy or radiotherapy is prohibited while the patient is receiving trial treatment. Steroids should be weaned down to ≤10mg/day (prednisolone; or the equivalent dose of other steroids) within 7 days prior to starting trial treatment.

8.9. Pharmacy Responsibilities

All pharmacy aspects of the trial at participating sites are the responsibility of the PI, who may delegate this responsibility to the local pharmacist or other appropriately qualified personnel, who will be the Pharmacy Lead. The delegation of duties must be recorded on the site staff delegation log.

Nivolumab supplied for the ANIMATE trial are for eligible ANIMATE trial patients only and must not be used outside the context of this protocol.

8.9.1. Temperature Excursions

All temperature excursions outside the storage conditions specified in the IB/Summary of Drug Arrangements/labels must be reported to UCL CTC as per the 'Pharmacy Procedure for Reporting Temperature Excursions' (see Pharmacy Site File)

Upon identifying an excursion:

- all affected trial stock must be quarantined IMMEDIATELY
- a 'Notification of Temperature Excursion' form must be completed and e-mailed to [contact] or faxed to [name].

Please note that UCL CTC must be informed immediately if a patient has been administered drug affected by a temperature excursion.

8.9.2. IMP accountability

The Pharmacy Lead must ensure that appropriate records are maintained.

These records must include accountability for each drug including: receipt, dispensing, reconciliation and destruction of unused medication (on sponsor authorisation). Accountability forms will be supplied, and must be used, unless there is prior agreement from UCL CTC to use alternative in-house records.

Copies of completed drug accountability logs must be submitted to UCL CTC for all trial patients upon request. Also refer to section 14.1 (Central Monitoring).

8.10. Clinical Management after Treatment Discontinuation

Clinical management following treatment discontinuation will be at the treating clinician's discretion.

If a patient discontinues trial treatment early, they will remain on trial for follow up purposes unless they explicitly withdraw consent. Also refer to sections 9 (Assessments) and 15 (Withdrawal of Patients) for further details regarding treatment discontinuation, patient withdrawal from trial treatment and withdrawal of consent to data collection.

8.11. Drug Provision after the End of the Trial

BMS will supply sufficient nivolumab for all eligible patients to receive up to 8 cycles of nivolumab. Patients will not continue treatment beyond 8 cycles, and there are no arrangements in place for supply following the end of the trial.

9. ASSESSMENTS

Please also see Schedule of Events table in Appendix 2

9.1. Pre-registration Assessments

Registration will take place before, during or within 14 days of completing the first 2 cycles of first or second line salvage treatment (4 cycles if treated with brentuximab vedotin). Patients must give written informed consent **before** any trial specific screening investigations may be carried out. The following assessments or procedures are required to evaluate the suitability of patients for the trial and must be carried out within 28 days prior to registration unless otherwise stated:

- Medical history
- Pregnancy test (serum or urine; women of childbearing potential; within 24 hours prior to registration)

Following study registration, the tumour block from the patient's lymphoma biopsy (preferably biopsy performed at time of relapse, or if unavailable the biopsy from their initial diagnosis) must be retrieved from the hospital's pathology archive and sent to the central laboratory (HMDS, Leeds). See section 10.1 and the Laboratory Manual for details.

9.2. Assessment of eligibility for nivolumab treatment

Following first or second line salvage, the patient will have assessments to verify they are eligible for treatment with Nivolumab.

The following investigations will be carried out within 18 days of cycle 2 first or second line salvage chemotherapy (cycle 4 if being treated with brentuximab vedotin) ±3 days:

- PET-CT scan (PET0; to be carried out as per trial requirements on an approved scanner; images to be sent to the PET core lab for central review – see the trial Imaging Manual for details).
- Contrast enhanced CT scan (ceCT). If feasible, this should be performed at the same imaging session as the PET-CT. If performed at the same session, the ceCT scan should be performed after the low dose PET-CT (see trial Imaging Manual for details).

The following investigations will be carried out up to 3-6 weeks after last administration of cycle 2 first or second line salvage chemotherapy (cycle 4 if being treated with brentuximab vedotin) if PET-CT was positive (Deauville 4-5):

- Medical history
- Clinical examination
- Weight
- Full blood count with differential (must be performed at least 3 weeks post completion of salvage)
- Biochemistry (ALT/AST, total bilirubin, alkaline phosphatase, urea, creatinine, calcium, magnesium, sodium, potassium, LDH, albumin, urate, glucose) (must be performed at least 3 weeks post completion of salvage)
- Creatinine clearance (calculated by Cockroft-Gault method)
- Tests for autoimmune conditions (amylase, lipase, thyroid function tests, adrenocorticotrophic hormone (ACTH))
- Electrocardiogram (ECG)
- Echocardiogram (if clinically indicated e.g. abnormalities on ECG)

- Lung function test
- ECOG performance status
- Hepatitis B & C serology:
 - -hepatitis B surface antigen (HBsAg)
 - o hepatitis B surface antibody (HBsAb) if standard locally
 - hepatitis B core antibody (HBcAb)
 - hepatitis B antibodies or hepatitis B DNA (HBV DNA) IF hepatitis B core antibody positive
 - hepatitis C antibodyies or hepatitis C DNA (HCV DNA) (local standard test to be used))

The following investigation is to be carried out within 24 hours prior to confirming eligibility for treatment:

Pregnancy test (serum or urine; women of childbearing potential)

The table below summarises the permitted timeframes for performing eligibility assessments. NB treatment with nivolumab must not be started until eligibility for trial treatment has been confirmed.

Week post first or second line salvage	1	2	3	4	5	6
PET CT ¹						
Other treatment eligibility tests ²						

Notes

9.3. Assessments prior to cycle 1 of Nivolumab

The following investigations are to be performed within 24 hours prior to starting Nivolumab:

Pregnancy test (urine or serum; WOCBP only)

The following investigations are to be performed within 3 days prior to starting Nivolumab:

- Clinical examination, including documentation of baseline adverse events
- Full blood count with differential*
- Biochemistry (ALT/AST, total bilirubin, alkaline phosphatase, urea, creatinine, calcium, magnesium, sodium, potassium, LDH, albumin, urate, glucose) *
- Thyroid function tests (TSH & Free T4; Free T3 to be performed if TSH/Free T4 abnormal)
- Test for autoimmune conditions (Amylase, lipase, ACTH)
- Blood samples to be taken and sent to the central laboratory at the Weatherall Institute of Molecular Medicine, Oxford (see section 10.2 and Laboratory Manual for details)

The following investigations must be carried out on the day of nivolumab administration:

Oxygen saturation measured by pulse oximetry at rest

^{1 =} PET CT to be performed 18 days after last administration of salvage treatment ±3 days

^{2 =} FBC and biochemistry must be performed at least 3 weeks after after last administration of cycle 2 salvage treatment (or cycle 4 of brentuximab vedotin) to allow time for count recovery. For WOCBP, a pregnancy test is required within 24 hours prior to starting nivolumab.

^{*} Do not need to be repeated if investigations for confirmation of eligibility (see section 9.2) were performed within 3 days prior to starting Nivolumab

9.4. Assessments during Treatment

During treatment the patient should be seen every 2 weeks and the following assessments performed within 3 days prior to the start of each cycle:

- Clinical examination
- Full blood count with differential
- Biochemistry (ALT/AST, total bilirubin, alkaline phosphatase, urea, creatinine, calcium, magnesium, sodium, potassium, LDH, albumin, urate, glucose)
- Tests for autoimmune conditions (amylase, lipase, ACTH)
- Cycles 3, 5 & 7: pregnancy test (urine or serum; WOCBP only)
- Cycle 4 and cycle 7: Thyroid function tests (TSH & Free T4; Free T3 to be performed if TSH/Free T4 abnormal)
- Adverse event assessment

The following investigations must be carried out on the day of nivolumab administration:

Oxygen saturation measured by pulse oximetry at rest

Blood samples for translational research

Blood samples are to be taken and sent to the central laboratory at the Weatherall Institute
of Molecular Medicine, Oxford within 3 days prior to the start of cycles 2, 4, 6 and 8, and
at the 1 month post-treatment visit (see section 10.2 and Laboratory Manual for more
details)

Scanning required after cycle 4

- PET-CT scan to be carried out on cycle 4, day 11-13 as per trial requirements on an approved scanner, and images sent to the PET core lab for central review (PET4; see trial Imaging Manual for details).
- Contrast enhanced CT scan (ceCT). If feasible, this should be performed at the same imaging session as the PET-CT. If performed at the same session, the ceCT scan should be performed after the low dose PET-CT (see trial Imaging Manual for details).

9.5. Assessments on Completion of Trial Treatment

For patients who withdraw from trial treatment for any reason during cycles 1-3 of nivolumab:

• Lung function test (to be performed as soon as possible after decision to stop trial treatment, and before the next line of treatment begins)

For patients in CMR (Deauville 1-3) or with progressive disease after 4 cycles of nivolumab

 Lung function test (to be performed as soon as possible after receiving the PET-CT central review result)

If a biopsy is performed to confirm progressive disease, please send the block to HMDS, Leeds (see section 10).

For patients who withdraw from trial treatment for any reason during cycles 5-7:

- PET-CT scan to be carried out at least 11-13 days after last trial treatment administration, as per trial requirements on an approved scanner, and images sent to the PET core lab for central review (see trial Imaging Manual for details).
- Lung function test (to be performed as soon as possible after decision to stop trial treatment, and before the next line of treatment begins)

For patients who complete all 8 cycles of trial treatment:

- PET-CT scan to be carried out on cycle 8, day 11-13 as per trial requirements on an approved scanner, and images sent to the PET core lab for central review (PET8; see trial Imaging Manual for details).
- Contrast enhanced CT scan (ceCT). If feasible, this should be performed at the same imaging session as the PET-CT. If performed at the same session, the ceCT scan should be performed after the low dose PET-CT (see trial Imaging Manual for details).
- Repeat lymph node biopsy (if patient is PET positive and has consented for a repeat biopsy). Block to be sent to central laboratory (HMDS) (see section 10.1 and Laboratory Manual for details)
- Lung function test (to be completed 10 days after last nivolumab administration ±2 days)

9.6. Assessments During Follow Up

Patients will be followed up for a minimum of 3 years. All efforts should be made by the Site to contact the patient's GP to assess their condition, if a patient fails to attend a clinic or cannot be followed up at site.

9.6.1. Patients who are ineligible for Nivolumab

Patients will be seen as follows:

- 3 months after PET0 scan (i.e. scan performed at end of first or second line salvage)
- 6 months after PET0 scan
- 9 months after PET0 scan
- 12 months after PET0 scan
- Annually thereafter

The following investigations will be performed:

• Remission status assessment (investigations as per local protocols).

9.6.2. Patients who receive nivolumab

Follow up in year 1 post treatment

Patients will be seen approximately once a month for the first 3 months, and every 3 months thereafter.

The following tests will be performed **1 month**, **2 months and 3 months** post treatment (30, 60 & 90 days after the last dose of Nivolumab respectively (±3 days)):

- Clinical examination
- Full blood count with differential
- Biochemistry (ALT/AST, total bilirubin, alkaline phosphatase, urea, creatinine, calcium, magnesium, sodium, potassium, LDH, albumin, urate, glucose)

- Tests for autoimmune conditions (amylase, lipase, ACTH)
- Thyroid function tests (TSH & Free T4; Free T3 to be performed if TSH/Free T4 abnormal)
- Adverse event assessment
- Pregnancy test (urine or serum; WOCBP only)
- Remission status assessment (investigations as per local policy) 3 month timepoint only

Blood samples for translational research

Blood samples are to be taken and sent to the central laboratory at the Weatherall Institute
of Molecular Medicine, Oxford at the 1 month post-treatment visit (30 days post last dose
of nivolumab (±3 days); see section 10.2 and Laboratory Manual for more details)

The following tests will be performed at months 6, 9 and 12 post treatment:

- Clinical examination
- Full blood count with differential
- Biochemistry (U&E, LFTs)
- Remission status assessment (investigations as per local policy)
- Assessment for late toxicity of nivolumab

In addition, at month 12 post treatment, the following test will be carried out:

Lung function test

Follow up from year 2 post treatment onwards

Patients will be seen annually. The following investigations will be performed:

- Remission status assessment (investigations as per local protocols)
- Assessment for late toxicity of nivolumab

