3.2. Trial Endpoints

Primary endpoints

• Overall response rate (ORR) by PET-CT scan following 4-8 cycles of nivolumab

Secondary endpoints

- Progression-free survival (PFS) at 1 year
- Overall survival (OS) at 1 year
- Proportion of patients proceeding to SCT (ASCT or alloSCT)
- Safety & toxicity of nivolumab, particularly autoimmune toxicity
- OS and PFS stratified by partial metabolic response (PMR) versus complete metabolic response (CMR) on FDG-PET
- Transplant-related mortality and rate of serious complications of allogeneic transplant (grade 3-4 graft-vs-host disease, hyperacute graft-vs-host disease and steroid-responsive febrile syndrome)

Exploratory endpoints

- Correlate PET positive disease with histological evidence of disease on biopsy to establish biopsy negative PMR rate (subject to patient consent)
- Correlate disease response, as assessed by FDG-PET and histology, with serological markers, including serum TARC
- Evaluate the correlation between response to nivolumab and biological parameters e.g. PD-1 expression on Reed-Sternberg cells

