8.2. Treatment Summary

Patients for whom eligibility for treatment is confirmed (see section 7.2 for details) will receive 4-8 x 14-day cycles of nivolumab. Nivolumab 240mg will be administered on day 1 of each 14 day cycle. Dose banding is not permitted.

Trial treatment should begin within 4 weeks following the PET-CT scan to confirm eligibility for trial treatment (PET0).

	1	2	3	4	5	6	7	8	9	10	11	12	13	14
Nivolumab 240mg IV	Х													

Patients will have a PET-CT scan after 4 cycles (PET4). This should be performed on cycle 4, day 11-13 to allow time for central review before the cycle 5 day 1 visit would be due. Please note that patients must not proceed to cycle 5 prior to receipt of the PET4 central review report.

- If PET-negative (Deauville 1-3), they will stop nivolumab. Further management will be at the discretion of the treating clinician and the patient will be followed up as per the trial protocol (see section 9.6.2).
- If the scan shows disease progression, they will stop nivolumab and have further salvage at their treating clinician's discretion. They will enter into annual follow up for the trial.
- If the scan is positive (Deauville 4-5) but there is no evidence of disease progression, the patient will have a further 4 cycles of nivolumab. Following this, they will be followed up as per the trial protocol (see section 9.6.2).

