18.2.2. Analysis of secondary endpoints and secondary analyses

Survival endpoints:

Progression free survival (PFS)

PFS time will be measured from the date of the PET scan after first or second line salvage treatment (PET0) until the date of progression or death (whichever comes first). Patients who are alive and progression free will be censored at the date last seen.

Overall survival (OS)

OS time will be measured from the date of the PET scan after first or second line salvage treatment (PET0) until the date of death. Patients who are alive will be censored at the date last seen.

Analysis of PFS and OS will take place once we have 1 year follow-up for all patients. Kaplan Meier survival analyses will be used for both.

Subgroup analyses will be performed for responders and non-responders i.e. do patients with a PMR do worse than those with a CMR after nivolumab treatment. Kaplan Meier survival analysis and Cox regression may be used, although this will be dependent on the numbers of patients with a response and the numbers of events.

PFS and OS will also be analysed by further treatment i.e. did the patient go on to have an allograft or autograft, though we acknowledge that numbers will be very small so analyses will be descriptive.

CMR/PMR rates

Proportions of patients achieving CMR and PMR will also be presented.

Adverse events:

Analysis will focus on grade 3/4 adverse events. The worst grade seen per patient will be shown for each event type.

AESIs will be reported in more detail, with autoimmune events of any grade presented. All analysis will be descriptive.

Transplant related mortality and the rate of serious complications of allo SCT will presented, though again, it is likely only descriptive statistics will be used.

Other analyses:

The association between pre-nivolumab biological parameters and response to nivolumab will be investigated. As numbers will be very small mostly descriptive statistics will be used i.e. numbers and percentages will be presented for binary/categorical data and means and medians (with ranges) for continuous measurements.

We will also look at changes in TARC levels in responders and non-responders.

PET negative patients not treated with nivolumab

We will look at PFS, OS and subsequent treatments for patients who are PET negative following first or second line salvage treatment (i.e. at PET0).

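### One-year PFS is counted from PET0, but treated patients' remission checks are counted from the last nivolumab dose, so the last scheduled check falls 3-11 weeks before the 1-year point and the estimate can only drift upward

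*Protocol*

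**What the plan says.** Section 3.2 of the protocol lists "Progression-free survival (PFS) at 1 year" as a secondary endpoint. Section 18.2.2 fixes the origin: "PFS time will be measured from the date of the PET scan after first or second line salvage treatment (PET0) until the date of progression". Deaths count as events too. On timing it adds: "Analysis of PFS and OS will take place once we have 1 year follow-up for all patients".

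For treated patients, section 9.6.2 and Appendix 2.1 count follow-up from the last nivolumab dose. Remission status is first assessed at the 3-month visit (90 days after the last dose), and then: "The following tests will be performed at months 6, 9 and 12 post treatment". The means of assessment is left to local policy.

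For patients who do not receive nivolumab, section 9.6.1 uses the PET0 clock and includes a check at "12 months after PET0 scan". Nothing in the protocol schedules a check at that time for treated patients.

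The lag between the two clocks comes from section 8.2: "Trial treatment should begin within 4 weeks following the PET-CT scan to confirm eligibility for trial treatment (PET0"), followed by 4 to 8 cycles of 14 days.

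**The concern.** An estimate of PFS at a fixed time is most trustworthy when disease status is ascertained at, or just before, that time. Here the check nearest to 1 year depends on when the last dose was given, which itself depends on the start lag and the number of cycles. A progression that produces no symptoms and arises between the last check before 1 year and the first check after it takes the date of the later check. The patient then counts as progression-free at 1 year. The error runs in one direction only.

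Two things are at stake. The 1-year PFS of the treated cohort may be somewhat too high. And it is read on a different assessment schedule from the 1-year PFS of the PET-negative patients, who are checked at PET0 + 12 months.

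**Working it through.** The protocol states no expected 1-year PFS, so there is no figure of its own to reproduce. The check is calendar arithmetic followed by a simple bound.

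**Inputs from the protocol**
- Time origin PET0 (18.2.2); endpoint at 1 year (3.2), taken as day 365.
- Start of nivolumab at most 28 days after PET0 (8.2).
- Doses 14 days apart (8.2), so dose 4 falls 3 × 14 = 42 days after dose 1, and dose 8 falls 7 × 14 = 98 days after dose 1.
- Remission checks 3, 6, 9 and 12 months after the last dose (9.6.2), taken as +90, +183, +274 and +365 days.

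**Assumptions**
- Start no earlier than day 7 after PET0. PET0 is done 15-21 days after salvage ("PET CT to be performed 18 days after last administration of salvage treatment ±3 days"). The eligibility blood tests may not be done before day 21 after salvage, which is 0-6 days after PET0, and central confirmation then follows. A day-0 start would lengthen the 8-cycle gap to 12 weeks.
- No dose delays, and exactly 4 or 8 cycles.

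**Dates, in days after PET0**

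| | 4 cycles | 8 cycles |
|---|---|---|
| Last dose | 7+42 to 28+42 = 49-70 | 7+98 to 28+98 = 105-126 |
| 6-month check (+183) | 232-253 | 288-309 |
| 9-month check (+274) | 323-344 | 379-400 |
| 12-month check (+365) | 414-435 | 470-491 |
| Last check before day 365 | 323-344 | 288-309 |
| Gap to day 365 | 21-42 days (3-6 weeks) | 56-77 days (8-11 weeks) |

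**Upper bound on the bias.** Suppose every progression is found only at a scheduled check, and let S be the true 1-year PFS with constant hazard. Progressions in the gap of g days are then all missed at 1 year, and

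bias = S^((365 − g)/365) − S.

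At S = 0.60 (assumed):
- 4 cycles: g = 21 gives 1.8 points; g = 42 gives 3.6 points.
- 8 cycles: g = 56 gives 4.9 points; g = 77 gives 6.8 points.

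Over S = 0.50 to 0.80, the 8-cycle bound runs from about 3 to 8 points. If half of the progressions present clinically between checks, the figures are roughly halved.

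**Scale.** In a cohort of 30, 1.8 to 6.8 points is 0.5 to 2 patients. The standard error at S = 0.60 is √(0.6 × 0.4/30), about 9 points.

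**Which re-timed window works.** At S = 0.60:
- *Symmetric window, day 351-379, checks spread evenly.* Half fall by day 365, with a mean gap of 7 days and a bias of 0.6 points. The other half fall after it, so the last useful check is the 6-month one. For 4 cycles that gap is 112-133 days (10.2-12.3 points), so the average is about 5-6 points, worse than now. For 8 cycles the average of 0.6 and 4.9-6.8 is about 3-4 points.
- *Window of 4 weeks closing at day 365 (day 337-365).* The mean gap is 14 days: 0.60^(351/365) − 0.60 = 0.012, about 1 point in both groups.

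**The case against.** The strongest reply is that the figures are ceilings. Section 9.7 provides for investigation whenever progression is suspected, and section 12.5.2 requires confirmed progression to be reported within 72 hours at any time in the trial. Symptom-led progressions and deaths therefore keep their own dates. Most patients are expected to move on to transplant, so detection will depend heavily on local care, and the scheduled visits mandate no scan. Early progressions on nivolumab are caught at PET4 or PET8; if the hazard is front-loaded, fewer events fall just before month 12. The endpoint is secondary, has no threshold, and the bound is below one standard error. A last-dose clock also suits the toxicity follow-up that shares these visits. All of this stands and limits the size. It does not supply a check at the endpoint time, and sampling error does not cancel a shift that runs one way. An SAP, not seen here, can decide how dates are analysed but cannot add an assessment.

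Three stronger readings are tempting and are not supported:
- *That the comparison of CMR with PMR at 1 year is biased towards no difference.* Section 3.2 names OS and PFS stratified by response without a 1-year landmark, and 18.2.2 says only that Kaplan-Meier and Cox methods may be used, if numbers allow. Nor does response map onto cycle number: a patient in PMR or NMR at PET4 can reach CMR at PET8, so the CMR group can include 8-cycle patients.
- *That every treated patient goes unchecked for the same stretch before 1 year.* The 3-11 weeks is the length of an individual gap. On-schedule 4-cycle patients do have a check 3-6 weeks before 1 year.
- *That 2-7 points is the expected bias.* It is what would occur if no progression surfaced between visits.

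**Conclusion.** The point holds as a modest, avoidable misalignment. The protocol itself sets the two clocks, and for treated patients nothing ties a remission check to PET0 + 12 months. With an on-schedule course started 7-28 days after PET0, the last check precedes 1 year by 8-11 weeks after 8 cycles and by 3-6 weeks after 4. Delays, or stopping at another cycle, can put an individual's gap anywhere from 0 to about 13 weeks, the length of the 3-month interval.

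The direction is upward. The size is at most about 5-7 points (8 cycles) and 2-4 points (4 cycles), given an assumed true 1-year PFS of 60%, constant hazard and detection only at scheduled checks. Treated and PET-negative 1-year PFS should not be read side by side as though assessed on one schedule. The primary ORR is not touched.

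**What to change.** In section 9.6.2 and Appendix 2.1, time the remission-status part of the 9-month post-treatment visit to fall on or shortly before PET0 + 12 months, for example within the 4 weeks up to and including that date. Avoid a symmetric ±2-week window, for the reason shown in the calculation. Toxicity follow-up can stay on the last-dose clock where that is needed.

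Cost: wording in two places and no added visit, provided the two parts of the visit are kept together. The check comes forward by about 2-9 weeks after 8 cycles (day 379-400 to day 337-365). After 4 cycles it is unchanged or up to about 6 weeks later (day 323-344 to day 337-365). The downside is that in 4-cycle patients the interval since the 6-month check can lengthen from 13 weeks to at most about 19 (day 232 to day 365 is 133 days). Re-timing does not guarantee imaging, since the method of assessment remains local policy, but it does give each treated patient a recorded disease status close to the endpoint time.
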